## SCHEMA

## LIST OF ABBREVIATIONS AND DEFINITION OF TERMS

MAA	Macro aggregated albumin
IRB	Institutional Review Board
IV	Intravenous
IA	Intra-arterial
SIRT	Selective internal radiation therapy
PET/CT	Positron emission tomography – computed tomography
ROC	Receiver-Operative-Characteristic
SUV	Standardized Uptake Value

## 1. OBJECTIVES

### 1.1 Primary Objective

- To evaluate the image quality of  $^{90}\text{Y}$  PET/CT post SIRT images as compared to  $^{99\text{m}}\text{Tc}$  MAA SPECT/CT.

### 1.2 Secondary Objective

- To determine the superior accuracy in both distribution and dosimetry of  $^{90}\text{Y}$  PET/CT post SIRT imaging compared to  $^{99\text{m}}\text{Tc}$  MAA planar and SPECT/CT imaging

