## 2. BACKGROUND

### 2.1 Preliminary information

Yttrium-90 ( $^{90}\text{Y}$ ) selective internal radiation therapy (SIRT) is a rapidly emerging radionuclide treatment modality for hepatic liver malignancy. The majority of patients with hepatocellular carcinoma are being treated with glass microspheres (TheraSphere®; Biocompatibles Inc., London, UK), while most patients with liver metastasis are being treated with resin microspheres (SIR-Spheres®; Sirtex Medical Limited, Lane Cove, Australia). SIRT leads to improvements in progression free and overall survival (1-4). Complications are either caused by inadvertent deposition of radioactive microspheres outside the liver, in the lungs (radiation pneumonitis) or in the gastrointestinal tract (gastrooduodenal ulceration), or by direct injury to functional liver parenchyma itself (5-7). Reported hepatic toxicity is mostly limited to symptoms related to the so-called post-radioembolization syndrome including mild pain, nausea, vomiting and fatigue, but may include a more serious clinical syndrome, called radioembolization induced liver disease (REILD), with liver insufficiency characterized by elevated liver enzymes and bilirubin, jaundice and ascites. REILD occurs in about 5% of the patients. It is difficult to treat and often fatal (8).

Individualized dose planning should aim for maximum treatment effect while keeping toxicity acceptably low. The current dose calculation methods however are based on empirical evidence with regard to both efficacy and safety, without established dose-response relationships (9). Resin microsphere activity doses are calculated by body surface area (BSA) and fractional liver involvement, while glass microsphere dose calculation is based on a whole liver partition model, derived from the medical internal radiation dosimetry pamphlet No. 17 (10). Although the latter method is more robust it does not take the radiation absorbed dose in the tumors or the normal liver tissue into account.

Despite success, there are currently no reliable methods to demonstrate and quantify distribution of the treatment doses to the target lesion(s).  $^{90}\text{Y}$  PET/CT represents a technological leap from  $^{90}\text{Y}$  bremsstrahlung SPECT/CT by coincidence imaging of low abundance internal pair production. However, image acquisition times are long and the resulting quality is suboptimal when using currently available PET/CT scanners.

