## **2.5 Study Design**

This is a non-randomized prospective trial. Patients who are referred to Nuclear Medicine and Interventional Radiology for  $^{99\text{m}}\text{Tc}$  MAA SPECT/CT followed by SIRT will be asked to have imaging done using the digital PET/CT scanner following the  $^{90}\text{Y}$  SIRT injection. This could be done during their mandatory 2-hr rest while lying flat (due to closure device), after their 2-hr rest period, or the next day after the participant's SIRT procedure. We will administer 50mL of IsoVue 370 contrast to the participant during the CT scan, if there are no contraindications. We will not inject additional radiopharmaceutical; instead, we will use the already administered  $^{90}\text{Y}$  from SIRT. This is possible because the digital PET/CT has very sensitive PET detectors. A very small amount of radiation (5 mSv) will be given by the attenuation correction CT scan in the second PET/CT.

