## **5.2 Details of Imaging (i.e. dynamic, static, number of scans, etc.)**

Patients will have  $^{99m}\text{Tc}$  MAA planar and SPECT/CT imaging as part of the standard SIRT planning protocol. These images are acquired after administration of 4 mCi of  $^{99m}\text{Tc}$  MAA in the Interventional Radiology suite. The patient will then be given  $^{90}\text{Y}$  Spheres (Glass or Resin), and after SIRT procedure, will be arrive to NM for digital PET/CT image acquisition with diagnostic contrast enhanced CT of the abdomen. We will be administering 50mL of iodinated contrast through IV during the CT scan. Next, PET images will be acquired in 3D mode using a single bed located over the liver, with a total acquisition time of approximately 30-minutes. The PET emission scan is corrected using the segmented attenuation data from the CT scan. The PET images are reconstructed both with a standard iterative algorithm (OSEM, two iterative steps, 28 subsets), as well as a regularized reconstruction algorithm provided by GE Healthcare. All images are reformatted into axial, coronal, and sagittal views and viewed with the software available in the Nuclear Medicine and Molecular Imaging Clinic (MIM Software, Cleveland, OH).

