## **5.3 Details of processing/analysis**

The  $^{99m}\text{Tc}$  MAA planar and SPECT/CT imaging and the PET/CT scans will be interpreted by ABNM certified Nuclear Medicine physicians. All investigators have significant clinical experience and will be blinded to the participant's medical history and the results of other imaging modalities. A consensus read will be obtained for each scan to assess image quality. Each lesion will be tabulated and a comparison of lesion detection and radiation absorbed dose by each scanner will be conducted.

Currently,  $^{99m}\text{Tc}$  MAA planar and SPECT/CT images only simulate  $^{90}\text{Y}$  radiopharmaceutical biodistribution within the liver and tumor(s). Incorporating SurePlan software (MIM) to analyze the PET/CT images will determine final dose-volume histogram (DVH) within the liver and tumor (s) post  $^{90}\text{Y}$  injection. Additionally,  $^{90}\text{Y}$  PET/CT and  $^{99m}\text{Tc}$  MAA planar and SPECT/CT biodistribution images can be compared to evaluate  $^{99m}\text{Tc}$  MAA simulation accuracy. Results of this image comparison could potentially impact clinical decision-making moving forward. This information will be reported and shared with the referring physicians involved in the care of the patient.

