## **10.5 Secondary outcome measure**

We will assess the radiopharmaceutical distribution and dosimetry accuracy of  $^{90}\text{Y}$  PET/CT by comparing visual distribution discrepancies (if any) and numerical values calculated by SurePlan from both  $^{99m}\text{Tc}$  MAA SPECT/CT and  $^{90}\text{Y}$  PET/CT images.

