## **10.6 Measurement Methods**

We will use SurePlan software to edge-contour and calculate tumor radiation absorbed dose values in both  $^{99m}\text{Tc}$  MAA SPECT/CT and  $^{90}\text{Y}$  PET/CT images. This software will convert counts/pixel on the images to radiation absorbed dose measure in Gray.

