## **10.8 Response Review**

After radiation absorbed dose is measured in both  $^{99m}\text{Tc}$  MAA SPECT/CT and  $^{90}\text{Y}$  PET/CT images, the values will be compared on a lesion-by-lesion basis.

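### The secondary objective claims superior accuracy for 90Y PET/CT, but the plan compares it only with MAA imaging and names no independent reference, so the data can estimate agreement and not superiority

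*Combined protocol and SAP*

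**What the plan says.** All references are to the combined protocol and SAP.

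- **Objective.** Section 1.2: "To determine the superior accuracy in both distribution and dosimetry of" 90Y PET/CT after SIRT, against MAA planar and SPECT/CT imaging.
- **Outcome.** Section 10.5 assesses the distribution and dosimetry accuracy of PET/CT "by comparing visual distribution discrepancies (if any) and numerical values calculated by SurePlan from both" MAA SPECT/CT and PET/CT.
- **Measurement.** Section 10.6 uses one software package for both image sets: "This software will convert counts/pixel on the images to radiation absorbed dose measure in Gray".
- **Comparison.** Section 10.8: "the values will be compared on a lesion-by-lesion basis". Section 5.3 adds: "Each lesion will be tabulated and a comparison of lesion detection and radiation absorbed dose by each scanner will be conducted".
- **What each scan shows.** Under section 2.5 no further tracer is injected for PET/CT: "instead, we will use the already administered" 90Y. Section 5.3 describes MAA imaging as only a simulation of the 90Y distribution, and says the two can be compared to judge how accurate that simulation was.
- **Field.** Section 5.2: "PET images will be acquired in 3D mode using a single bed located over the liver".
- **Analysis.** Section 11.5 declares that the study needs no statistical analysis, because the two modalities differ in nature.

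**The concern.** Accuracy means closeness to a true value, and superior accuracy means being closer to it than the comparator. The plan observes two quantities, the MAA-based and the PET-based result, and compares them with each other. It names no phantom, known-activity check, tissue measurement or other third quantity for either modality. Section 8.2 mentions double-checking doses, but the plan does not use administered activity to test the PET dosimetry. The historical PET/CT data in 2.1 and 2.4 concern speed and image quality only.

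If the result is reported under the wording of 1.2, a difference between PET and MAA would be read as PET being right and MAA wrong. It could instead reflect real redistribution between two separate administrations, error in the PET dose scale, error in the MAA dose scale, or a mixture. Section 5.3 says the comparison may influence clinical decisions and will go to referring physicians, so the label put on the difference matters. Since 11.5 plans no analysis, nothing in the plan limits that reading.

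Two gaps go with this. Section 10.5 gives no definition of a visual discrepancy. Planar imaging appears in 1.2 and in the 5.3 comparison but is absent from 10.5 to 10.8.

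**Working it through.** **1. The plan's own figures.** There is no power, margin, SD or precision figure to reproduce. The only number is accrual: 25 per year (11.3) × 3 years (36 months, 3.4.1) = 75, which matches the stated 75 but is not a precision argument.

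**2. What the comparison identifies.** Let T be the true mean delivered 90Y tumor dose, which is not observed.

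- PET mean = T + PET error
- MAA mean = T + redistribution + MAA error

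The unknowns are T, PET error, redistribution and MAA error. The coefficient rows are [1,1,0,0] and [1,0,1,1]: rank 2 for 4 unknowns. Subtracting removes T:

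PET − MAA = PET error − redistribution − MAA error.

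This combination can be estimated, but its parts cannot be separated. More patients narrow its interval without separating them.

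**3. Illustration (all values assumed, log-dose scale).** Give both modalities an error variance of 0.085.

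| | True mean | PET bias | MAA bias | PET mean | MAA mean | RMSE PET | RMSE MAA |
|---|---|---|---|---|---|---|---|
| A | 4.6 | 0 | −0.2 | 4.6 | 4.4 | √0.085 = 0.292 | √(0.085 + 0.2²) = 0.354 |
| B | 4.4 | +0.2 | 0 | 4.6 | 4.4 | 0.354 | 0.292 |

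PET is the more accurate in A and MAA in B. The data look the same in both: mean difference 0.20, SD of differences √(0.085 + 0.085) = 0.412, 95% limits of agreement 0.20 ± 1.96 × 0.412 = −0.61 to 1.01. In A, the whole MAA bias could be redistribution with no measurement error.

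Unequal random errors widen the contrast but leave the paired result unchanged. With PET unbiased (SD 0.1) and MAA biased by −0.2 (SD 0.4), RMSE is 0.10 for PET and √(0.16 + 0.04) = 0.45 for MAA. Reversing the roles reverses the RMSEs, while the mean difference stays 0.20 and its SD √(0.01 + 0.16) = 0.41.

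In that unequal case the spread of each modality's own values does differ, so one might look to variances for help. If the errors were independent of T and of each other, and both scales had unit slope, Var(PET) − Cov(PET, MAA) would isolate PET's random error. That says nothing about bias, and the plan gives no basis for those conditions.

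**4. Feasibility of an agreement analysis.** Assume n = 75 evaluable patients and total SD of the differences = 1.

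*One lesion each:*
- Mean difference: 1.96 × √(1/75) = 0.226 SD.
- Each limit of agreement: 1.96 × √(1/75 + 1.96²/(2 × 74)) = 0.389 SD.

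*Three lesions each (m = 3), within-patient correlation r:* Var(mean) = (r + (1 − r)/m)/n. Var(total variance) = 2(mr + 1 − r)²/(m²(n − 1)) + (1 − 1/m)² × 2(1 − r)²/(n(m − 1)), and Var(SD) is a quarter of that. The limit's half-width is 1.96 × √(Var(mean) + 1.96² Var(SD)).

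| r | Mean difference | Each limit |
|---|---|---|
| 0.3 | 0.165 | 0.258 |
| 0.5 | 0.185 | 0.290 |
| 0.8 | 0.211 | 0.347 |

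*Share of patients with a visual discrepancy (Wilson 95% CI, counts assumed):* 8/75 gives 5.5–19.7%, 15/75 gives 12.5–30.4%, and 30/75 gives 29.7–51.3%.

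**The case against.** The strongest reply is that PET/CT images the 90Y actually delivered while MAA only simulates it, so PET/CT is the natural reference. Section 5.3 already frames the comparison as a check on MAA, and the plan contains no superiority test, margin or success rule. On that view the fault is one objective bullet and one phrase in 10.5.

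Much of this stands. PET/CT is a reasonable comparator for how well MAA predicted delivery, the aim in 5.3 is sound, and this is a secondary objective with no decision attached. But that reply supports a statement about MAA, whereas 1.2 and 10.5 make a statement about PET/CT. Its Gray values are themselves derived, by a software conversion not checked against a known quantity. Section 5.2 also reconstructs the PET data by two algorithms, and 10.6 does not say which one supplies the dose.

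Three stronger readings may tempt a reader and should be resisted:

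- *That the protocol itself shows PET dosimetry to be unreliable.* Section 2.1 does say reliable quantification is currently lacking, but this is the motivation for the study. It goes on to present 90Y PET/CT as an advance and aims its criticism at existing scanners. It is weak evidence about the digital scanner.
- *That PET–MAA differences are known to contain redistribution.* The design cannot identify redistribution; differences may include it.
- *That planar imaging should be dropped because 10.6 computes dose only from SPECT/CT and PET/CT.* Section 1.2 covers distribution as well as dose, and 5.3 includes planar images in the distribution comparison. A dose-only rule does not justify the removal.

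**Conclusion.** The concern holds as a mismatch between objective and design. The planned data can estimate agreement, or MAA's prediction of post-treatment PET/CT. They cannot establish that PET/CT is the more accurate. This conclusion rests on the text and on the absence of a reference, not on any assumed number.

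The defect has no numerical size. The half-widths of about 0.23 SD and 0.39 SD show only that an agreement analysis is feasible. They assume that all 75 enrolled patients give evaluable pairs with one lesion each, and they are in SD units because the documents give no SD.

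A reader might infer that the comparison is worthless. It is not: the scans answer the question in 5.3 well. The change should be made because it alters what the trial may conclude, at little cost.

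**What to change.** 1. **Reword 1.2 and 10.5**, for example: *To estimate agreement between MAA-predicted and 90Y PET/CT-measured post-treatment distribution and tumor absorbed dose, within the liver field imaged by the single PET bed.*
2. **Give this outcome an analysis in 11.5**, in place of the statement that none is required:
   - *Dose:* mean paired per-lesion difference (PET minus MAA SPECT/CT) and 95% limits of agreement, on the log scale if differences grow with dose. Allow for several lesions per patient by a random patient effect or a patient-level bootstrap. Report from the 5.3 lesion table how many lesions were seen on only one scan.
   - *Distribution:* proportion of patients with a visual discrepancy, with a 95% CI, defined before reading. Sections 5.3 and 10.4 keep readers blind to the other scan, so say how the discrepancy is obtained: either by comparing the existing blinded reads, or by a side-by-side review by the same readers after those reads are locked.
3. **State the limit on interpretation:** differences may include real redistribution between the two administrations as well as error in either modality, and are not attributed to one of them.
4. **Reconcile planar imaging** between 1.2/5.3 and 10.5–10.8, for example by including it in the visual distribution comparison only.

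If the sponsor wishes to keep an accuracy claim, the alternative is to name an independent reference in 10.5, such as a phantom of known 90Y activity, and confine the claim to what that tests. This adds measurement work outside the present plan.

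The main route needs text edits, one written definition and a short analysis, with no new patient scans. A side-by-side review would add some reading time. The trial gives up a superiority claim that its design cannot support.

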## 2. BACKGROUND

### 2.1 Preliminary information

Yttrium-90 ( $^{90}\text{Y}$ ) selective internal radiation therapy (SIRT) is a rapidly emerging radionuclide treatment modality for hepatic liver malignancy. The majority of patients with hepatocellular carcinoma are being treated with glass microspheres (TheraSphere®; Biocompatibles Inc., London, UK), while most patients with liver metastasis are being treated with resin microspheres (SIR-Spheres®; Sirtex Medical Limited, Lane Cove, Australia). SIRT leads to improvements in progression free and overall survival (1-4). Complications are either caused by inadvertent deposition of radioactive microspheres outside the liver, in the lungs (radiation pneumonitis) or in the gastrointestinal tract (gastrooduodenal ulceration), or by direct injury to functional liver parenchyma itself (5-7). Reported hepatic toxicity is mostly limited to symptoms related to the so-called post-radioembolization syndrome including mild pain, nausea, vomiting and fatigue, but may include a more serious clinical syndrome, called radioembolization induced liver disease (REILD), with liver insufficiency characterized by elevated liver enzymes and bilirubin, jaundice and ascites. REILD occurs in about 5% of the patients. It is difficult to treat and often fatal (8).

Individualized dose planning should aim for maximum treatment effect while keeping toxicity acceptably low. The current dose calculation methods however are based on empirical evidence with regard to both efficacy and safety, without established dose-response relationships (9). Resin microsphere activity doses are calculated by body surface area (BSA) and fractional liver involvement, while glass microsphere dose calculation is based on a whole liver partition model, derived from the medical internal radiation dosimetry pamphlet No. 17 (10). Although the latter method is more robust it does not take the radiation absorbed dose in the tumors or the normal liver tissue into account.

Despite success, there are currently no reliable methods to demonstrate and quantify distribution of the treatment doses to the target lesion(s).  $^{90}\text{Y}$  PET/CT represents a technological leap from  $^{90}\text{Y}$  bremsstrahlung SPECT/CT by coincidence imaging of low abundance internal pair production. However, image acquisition times are long and the resulting quality is suboptimal when using currently available PET/CT scanners.

More than a decade ago, multimodality imaging was introduced into clinical routine with the development of the PET/CT. Since then, PET/CT has been widely accepted in clinical imaging and has emerged as one of the main cancer imaging modalities. With the recent development of combined PET/MRI systems for clinical use, a promising new PET detector technology using silicon photomultiplier tubes has become available. The combination of functional information delivered by highly sensitive novel PET detectors with the morphologic imaging of

CT offers exciting possibilities for clinical applications as well as basic research. However, the differences between standard and digital PET detectors are fundamental. Digital PET/CT is expected to show advantages over standard PET/CT by decreasing required dose of PET radiopharmaceuticals, higher sensitivity and temporal resolution. However, as of now, only assumptions can be made about the future clinical role of digital PET/CT, as data about the performance of digital PET/CT in the clinical setting are still limited (11). The first ever GE-made digital PET/CT scanner worldwide will be installed in the Nuclear Medicine and Molecular Imaging Clinic. This novel digital PET/CT may allow for faster and higher quality images of the therapy agent distribution when compared to historical published data from standard PET/CT.

## **2.2 Study Agent/Device**

Digital PET/CT Scanner

## **2.3 Clinicaltrials.gov**

This study will be registered on clinicaltrials.gov

## **2.4 Rationale**

Selective internal radiation therapy (SIRT) is a form of radiation therapy used in interventional radiology to treat cancer. It is used for selected patients with unresectable cancers, those that cannot be treated surgically, especially hepatic cell carcinoma or metastasis to the liver. Despite success, there are currently no reliable methods to demonstrate and quantify distribution of the treatment doses to the target lesion(s).  $^{90}\text{Y}$  PET/CT represents a technological leap from  $^{90}\text{Y}$  bremsstrahlung SPECT/CT by coincidence imaging of low abundance internal pair production. However, image acquisition times are long and the resulting quality is suboptimal when using currently available PET/CT scanners. However, the first ever GE-made digital PET/CT scanner worldwide will be installed in the Nuclear Medicine and Molecular Imaging Clinic. This novel digital PET/CT may allow for faster and higher quality images of the therapy agent distribution when compared to historical published data from standard PET/CT.

## **2.5 Study Design**

This is a non-randomized prospective trial. Patients who are referred to Nuclear Medicine and Interventional Radiology for  $^{99\text{m}}\text{Tc}$  MAA SPECT/CT followed by SIRT will be asked to have imaging done using the digital PET/CT scanner following the  $^{90}\text{Y}$  SIRT injection. This could be done during their mandatory 2-hr rest while lying flat (due to closure device), after their 2-hr rest period, or the next day after the participant's SIRT procedure. We will administer 50mL of IsoVue 370 contrast to the participant during the CT scan, if there are no contraindications. We will not inject additional radiopharmaceutical; instead, we will use the already administered  $^{90}\text{Y}$  from SIRT. This is possible because the digital PET/CT has very sensitive PET detectors. A very small amount of radiation (5 mSv) will be given by the attenuation correction CT scan in the second PET/CT.

# **3. PARTICIPANT SELECTION AND ENROLLMENT PROCEDURES**

## **3.1 Inclusion Criteria**

- Patient is  $\geq$  18 years old at the time of the scan
- Patient provides written informed consent
- Patient is referred for  $^{90}\text{Y}$  SIRT radioembolization of liver tumor(s)
- Patient is capable of complying with study procedures

- Patient is able to remain still for duration of imaging procedure (approximately 30 minutes total for digital PET/CT)

